3.5.2. Clinical laboratory evaluation

Summary statistics for laboratory tests will be presented at baseline and consecutive scheduled treatment visits. Laboratory tests results and changes from baseline to each visit and endpoint will be summarized using descriptive statistics. Shifts (below, within, and above the normal range) from baseline to each visit and endpoint will be summarized using subject counts. The incidence of clinically significant abnormal results will also be summarized for laboratory data using descriptive statistics.

3.5.3. Vital signs

Summary statistics for vital signs will be presented at baseline and consecutive scheduled treatment visits. Vital signs values and changes from baseline to each visit and endpoint will be summarized using descriptive statistics. The incidence of clinically significant abnormal values will be summarized for selected vital signs using descriptive statistics.

3.5.4. ECG

Summary statistics for ECGs will be presented at baseline and consecutive scheduled treatment visits. ECG values and changes from baseline to each visit and endpoint will be summarized using descriptive statistics. The incidence of clinically significant abnormal values will be summarized for selected ECGs using descriptive statistics.

4. STATISTICAL AND DATA HANDLING CONVENTIONS

4.1. Summary Statistics

The following statistical summaries will be presented for each type of data:

- Continuous variables will be summarized by descriptive statistics (number of subjects, mean, standard deviation (SD), median, minimum, and maximum values).
- Categorical variables will be summarized by frequency distributions (counts and percentages).
- Time-to-event data will be summarized by showing the number of subjects, number of subjects experiencing the event of interest, estimates of the median, first quartile and third quartile using the Kaplan Meier estimate as well as a 95% CI for the median

4.2. Visit Time Windows

Nominal visits will be used for analysis.

4.3. Missing Severity Assessment for Adverse Events

If severity is missing for an AE that started before the date of the first dose of IMP, an intensity of mild will be assigned. If severity is missing for an AE that started on or after the date of the first dose of IMP, a severity of severe will be assigned. The imputed values for severity assessment will be used for the incidence summary; the values will be shown as missing in the data listings.

4.4. Missing Causal Relationship to Investigational Product for Adverse Events

If the causal relationship to the IMP is missing for an AE that started on or after the date of the first dose of IMP, a causality of yes will be assigned. The imputed values for causal relationship to randomized treatment will be used for the incidence summary; the values will be shown as missing in the data listings.

4.5. Missing Date Information for Adverse Events

The following imputation rules only apply to cases in which the start date for an AE is incomplete (ie, partly missing).

Missing month and day

- If the year of the incomplete start date is the same as the year of the first dose of IMP, the month and day of the first dose of IMP will be assigned to the missing fields.
- If the year of the incomplete start date is before the year of the first dose of IMP, *31 Dec* will be assigned to the missing fields.
- If the year of the incomplete start date is after the year of the first dose of IMP, *01 Jan* will be assigned to the missing fields.

Missing month only

- If only the month is missing, the day will be treated as missing and both the month and the day will be replaced according to the above procedure.

Missing day only

- If the month and year of the incomplete start date are the same as the month and year of the first dose of IMP, the day of the first dose of IMP will be assigned to the missing day.
- If either the year of the incomplete start date is before the year of the date of the first dose of IMP or if both years are the same, but the month of the incomplete start date is before the month of the date of the first dose of IMP, the last day of the month will be assigned to the missing day.
- If either the year of the incomplete start date is after the year of the date of the first dose of IMP or if both years are the same, but the month of the incomplete start date is after the month of the date of the first dose of IMP, the first day of the month will be assigned to the missing day.

If the stop date is complete and the imputed start date as above is after the stop date, the start date will be imputed by the stop date.

If the start date is completely missing and the stop date is complete, the following algorithm will be used to impute the start date:

- If the stop date is after the date of the first dose of IMP, the date of the first dose of IMP will be assigned to the missing start date.
- If the stop date is before the date of the first dose of IMP, the stop date will be assigned to the missing start date.

4.6. Missing Date Information for Prior or Concomitant Medications

For prior or concomitant medications, incomplete (i.e. partially missing) start dates and/or stop dates will be imputed. When the start date and the stop date are both incomplete for a patient, the start date will be imputed first.

4.6.1. Incomplete Start Date

The following rules will be applied to impute the missing numeric fields for an incomplete prior or concomitant medication start date. If the stop date is complete (or imputed) and the imputed start date is after the stop date, the start date will be imputed using the stop date.

Missing month and day

- If the year of the incomplete start date is the same as the year of the first dose of IMP, the month and day of the first dose of IMP will be assigned to the missing fields.
- If the year of the incomplete start date is before the year of the first dose of IMP, *31 Dec* will be assigned to the missing fields.
- If the year of the incomplete start date is after the year of the first dose of IMP, *01 Jan* will be assigned to the missing fields.

Missing month only

- If only the month is missing, the day will be treated as missing and both the month and the day will be replaced according to the above procedure.

Missing day only

- If the month and year of the incomplete start date are the same as the month and year of the first dose of IMP, the day of the first dose of IMP will be assigned to the missing day.
- If either the year of the incomplete start date is before the year of the date of the first dose of IMP or if both years are the same, but the month of the incomplete start date is before the month of the date of the first dose of IMP, the last day of the month will be assigned to the missing day.
- If either the year of the incomplete start date is after the year of the date of the first dose of IMP or if both years are the same, but the month of the incomplete start date is after the month of the date of the first dose of IMP, the first day of the month will be assigned to the missing day.

4.6.2. Incomplete Stop Date

The following rules will be applied to impute the missing numeric fields for an incomplete prior or concomitant medication stop date. If the imputed stop date is before the start date (imputed or non-imputed start date), the imputed stop date will be equal to the start date.

Missing month and day

- If the year of the incomplete stop date is the same as the year of the date of last dose of IMP, the month and day of the date of the last dose of IMP will be assigned to the missing fields.
- If the year of the incomplete stop date is before the year of the date of last dose of IMP, *December 31* will be assigned to the missing fields.
- If the year of the incomplete stop date is after the year of the date of last dose of IMP, *January 1* will be assigned to the missing fields.

Missing month only

- If only the month is missing, the day will be treated as missing and both the month and the day will be replaced according to the above procedure.

Missing day only

- If the month and year of the incomplete stop date are the same as the month and year of the date of the last dose of IMP, the day of the date of the last dose of IMP will be assigned to the missing day.
- If either the year of the incomplete stop date is before the year of the date of last dose of IMP or if both years are the same but the month of the incomplete stop date is before the month of the date of the last dose of IMP, the last day of the month will be assigned to the missing day.

- If either the year of the incomplete stop date is after the year of the date of the last dose of IMP or if both years are the same but the month of the incomplete stop date is after the month of the date of the last dose of IMP, the first day of the month will be assigned to the missing day.

6. APPENDICES

APPENDIX I. TECHNICAL DETAILS FOR THE IMPLEMENTATION OF THE EXTENDED PLACEBO-BASED PATTERN MIXTURE MODEL VIA MULTIPLE IMPUTATION

The following steps will be taken to implement the extended placebo-based pattern mixture model via multiple imputation:

1. Carry out a Bayesian analysis for the Cox proportional hazards model with treatment group as an explanatory variable and with piecewise constant baseline hazard function. Let $h_0(t; \lambda) = \sum_{j=1}^J \lambda_j I(a_{j-1} \leq t < a_j)$ denote the piecewise constant baseline hazard function, where $a_0 = 0 < a_1 < \dots < a_{J-1} < a_J = \infty$ denotes a partition of the time axis. The cut points are chosen to have an approximately equal number of events in each interval. The number of intervals with constant baseline hazard rates, J , is set to strike a balance between the approximation to the unknown underlying baseline hazard function and the number of events in each interval. The hazard function for subject i is $h(t | X_i; \theta) = h_0(t; \lambda) \exp(\beta_1 X_{i1})$, where $X_{i1} = 1$ if subject i is in the ACP-01 group.
2. Take a posterior draw of the model parameters, $\tilde{\theta} = (\tilde{\lambda}, \tilde{\beta})$, from the Bayesian analysis.
3. For a subject who prematurely discontinued without meeting any of the event criteria during the study, impute the time to event after discontinuation, T_i , under the extended placebo-based pattern mixture model with sensitivity parameter ϕ , by equating the conditional survival probability at T_i given that the subject discontinued at C_i to a uniform random variable U_i , that is,

$$\exp \left\{ - \int_{C_i}^{T_i} h_0(t; \tilde{\lambda}) e^{(1-\phi)(\tilde{\beta}_1 X_{i1})} dt \right\} = U_i.$$

This equation can be easily solved by noting that the baseline hazard function $h_0(t; \lambda)$ is piecewise constant.

4. If the imputed event time exceeds the planned follow-up time for the subject, we manage the subject as having no event by the end of the planned follow-up time. Thus, the imputed complete data set has no subjects with premature discontinuation and has only administrative censoring at the planned follow-up time.
5. Apply the primary analysis model to the complete data set to obtain the parameter estimates and associated covariance matrix for a single imputation. The parameters are the log-rank test statistics for the log-rank test, and the log hazard ratios for the Cox model with treatment group as an explanatory variable.
6. Repeat Step 2 through Step 5 for m times to generate m sets of imputed complete-data parameter estimates and associated covariance matrices. Use the SAS procedure

MIANALYZE to combine results from m imputed data sets and draw inference about the treatment effect of ACP-01 versus placebo.

7. Vary the value of the sensitivity parameter $\phi \in \{0, 0.2, 0.4, 0.6, 0.8, 1\}$ in Step 3 to assess the robustness of the primary analysis results to the possible violation of the noninformative censoring assumption toward the informative censoring underlying the placebo-based pattern mixture model.

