3.3.2.2. Primary analysis

The primary efficacy analysis will be the comparison of the distribution of time to event between the two treatment arms using a stratified log-rank test at two-sided 5% level of significance, adjusted by study site and baseline prognostic factors.

The hazard ratio (HR) and its corresponding 95% confidence interval (CI) will be estimated using a stratified Cox proportional hazard (CPH) model. Time to event for each arm will be summarized using Kaplan Meier curves and further characterized in terms of the median and survival probabilities at 3, 6, 9, and 12 months along with the corresponding 2-sided 95% CI for the estimates.

Underlying assumptions of proportional hazards will be checked using Schoenfeld Residuals test and graphical methods (Log cumulative hazard curve). The adequacy of the proportional hazards (PH) assumption will also be confirmed by including a time dependent covariate for the active treatment group by log (time) interaction in the primary analysis model and testing it using 5% significance level. If proportionality is not observed, sensitivity analyses other than those already planned in the SAP could be carried out.

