3.3.2.3. Sensitivity analyses

In order to assess the consistency of the primary analysis of time to event, sensitivity analyses will be carried out including:

- An unstratified log-rank test and the hazard ratio along with the associated 95% CI resulting from an unstratified Cox model (only treatment arm in the model).
- An analysis based on PP analysis set

Three additional sensitivity analyses will be performed to assess the robustness of the primary analysis results to the possible violation of the noninformative censoring assumption. The first sensitivity analysis assumes that subjects who discontinued without meeting any of the event criteria during the study had an event instead of being censored. The second sensitivity analysis will be based on the delta-adjusted method examined by Zhao et al. (2014). The third sensitivity analysis is an extension of the placebo-based pattern mixture model proposed by Lu (2014, 2015). The placebo-based pattern mixture model assumes that subjects who discontinued from the ACP-01 arm would have an event after discontinuation similar to that of placebo. The extended placebo-based pattern mixture model uses a sensitivity parameter to characterize the gradual deviation from the noninformative censoring underlying the primary analysis toward the informative censoring underlying the placebo-based pattern mixture model. The extended placebo-based pattern mixture model sensitivity analysis for time-to-event data is described as follows:

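### The dropout imputation model in SAP Appendix I leaves out the strata and prognostic factors of the primary analysis, and step 5 does not say clearly whether the imputed data are re-analysed with them (minor)

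*SAP*

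**What the plan says.** - **Primary analysis (SAP 3.3.2.2).** Time to event is compared "using a stratified log-rank test at two-sided 5% level of significance, adjusted by study site and baseline prognostic factors". The hazard ratio is "estimated using a stratified Cox proportional hazard (CPH) model".
- **Imputation model (Appendix I, step 1).** The instruction is: "Carry out a Bayesian analysis for the Cox proportional hazards model with treatment group as an explanatory variable". The baseline hazard is piecewise constant and common to all subjects. The linear predictor contains only the treatment term, beta_1 X_i1. Step 3 draws each dropout's event time from this model.
- **Re-analysis (Appendix I, step 5).** It opens with "Apply the primary analysis model to the complete data set". The next sentence gives the parameters as the log-rank statistic and "the log hazard ratios for the Cox model with treatment group as an explanatory variable". Neither is called stratified or unstratified.
- **Grid (Appendix I, step 7).** "Vary the value of the sensitivity parameter" over 0, 0.2, 0.4, 0.6, 0.8 and 1. SAP 3.3.2.3 defines phi = 0 as the noninformative censoring that underlies the primary analysis.
- **Separate unstratified analysis (SAP 3.3.2.3).** An unstratified log-rank test is also planned, with a hazard ratio "resulting from an unstratified Cox model (only treatment arm in the model").

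**The concern.** The grid is meant to show how far the primary result moves as dropout becomes informative, so its phi = 0 row should sit close to the primary result. Two features work against that.

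First, under step 1 a dropout's imputed event time depends only on arm and time of dropout. A high-risk and a low-risk subject in the same arm who leave on the same day get the same distribution. The analysis conditions on factors that the imputation ignores.

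Second, if step 5 were programmed without strata, going from the primary hazard ratio to phi = 0 would change the model as well as impute data. A reader comparing the grid with the primary result could take that change for an effect of dropout.

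**Working it through.** **The plan's own figure.** SAP 1.3 gives 81% power for 51 events, HR 0.43, one-sided 2.5%; allocation is 2:1. By Schoenfeld's formula, sqrt(51 x 2/3 x 1/3) x |ln 0.43| - 1.960 = 3.367 x 0.844 - 1.960 = 0.881, so power is 81.1%. It is reproduced. It matters here because about 51 events is all the imputation model has to work with.

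**The models side by side.**
- Primary: h_s(t) = h_0s(t) exp(beta_1 X), with a separate baseline hazard for each stratum s.
- Step 1: h(t) = h_0(t) exp(beta_1 X), with one baseline hazard.
- Step 5: either form fits. In a stratified Cox model the strata enter through the baseline hazards, so treatment can be the only explanatory variable.

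**Large-sample size.** Assumed, because the documents do not give them: one binary risk factor with HR 2 or 4, about 10% event-free dropouts, and two dropout patterns (equal, or concentrated in the high-risk stratum). Conditional HR 0.43, 2:1, 12 months, six intervals, n = 120,000 per setting, imputation parameters held at their estimates.

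| Factor HR | Stratified primary | phi = 0, stratified | phi = 0, unstratified | phi = 1, unstratified |
|---|---|---|---|---|
| 2 | 0.433 | 0.435 | 0.456 | 0.485 |
| 2 | 0.424 | 0.426 | 0.448 | 0.480 |
| 4 | 0.428 | 0.441 | 0.520 | 0.544 |
| 4 | 0.429 | 0.444 | 0.516 | 0.542 |

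- Stratified step 5, shift at phi = 0 (column 3 minus 2): 0.002, 0.002, 0.013, 0.015. This comes from step 1 alone.
- Unstratified step 5, shift at phi = 0 (column 4 minus 2): 0.023, 0.024, 0.092, 0.087.
- Movement from phi = 0 to 1 (column 5 minus 4): 0.029, 0.032, 0.024, 0.026.

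So the unstratified shift is somewhat below the phi movement at factor HR 2 and more than three times it at factor HR 4.

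**Trial-size check.** 65 subjects, medians 3 and 7 months, 12 months of follow-up, four intervals, 10 imputations, 200 trials per scenario. Assumed: 6 or 15 sites, strata of site by ulcer (yes/no), dropout 8-9% or about 20%, site SD 0, 0.5 or 0.8, ulcer log HR 0, 0.5 or 0.9.

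- No prognostic effect: mean HR is 0.41-0.42 stratified and 0.41-0.43 unstratified, so there is no shift on average.
- Strongest effects: 0.39-0.43 stratified against 0.52-0.53 unstratified.
- Stratified step 5: the mean HR at phi = 0 stays near the primary. The largest gap is 0.410 - 0.385 = 0.025, with 15 sites, about 20% dropout and the strongest effects.
- Average absolute gap per trial between phi = 0 and the primary log HR: 0.04-0.14 stratified, 0.16-0.40 unstratified. The phi = 0 to 1 movement is 0.04-0.13. Much of the gap is noise: with no prognostic effect it is still 0.04-0.12 and 0.16-0.35.
- Mean standard error: 0.38-0.52 stratified, 0.31-0.33 unstratified. An unstratified grid would look more precise than the primary analysis.

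**Effect of matching step 1.** At 65 subjects with factor HR 4 and a stratified step 5, adding the factor to the imputation model cut the average per-trial gap at phi = 0 from 0.05-0.07 to 0.02-0.03 in log HR. The phi movement there was about 0.05-0.13.

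**The case against.** A reader might infer that Appendix I re-analyses the imputed data with an unstratified model. The documents do not establish that. Step 5 opens by calling for the primary analysis model, which is stratified. The words that follow only name the parameter passed on for pooling, and they suit a stratified Cox model. Where the SAP means an unstratified model, it says so in 3.3.2.3. This objection stands: the 0.02 to 0.09 shift is conditional on a possible reading.

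A reader might also infer that the grid cannot isolate dropout. It can. Only phi changes from row to row, so movement from phi = 0 to 1 reflects the dropout assumption under either reading. If the grid were unstratified, the planned unstratified Cox analysis would be a like-for-like comparator; at trial size phi = 0 lies within 0.02-0.03 of it in log HR on average. That too stands, although the SAP does not tell the reader to make that comparison.

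Finally, a sparse imputation model is defensible with about 51 events, and the analysis is supplementary. This limits how much should be added to step 1. It does not explain why factors thought important enough for the primary analysis are left out without comment.

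**Conclusion.** The concern holds in a limited form, as a cheap improvement of minor severity. The mismatch in step 1 is explicit and applies however step 5 is read. Step 5 is ambiguous, not wrong.

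Under the stratified reading, which its opening words favour, the shift in HR at phi = 0 is about 0.00 to 0.015 in large samples, with 0.025 the worst average at trial size and larger differences in single trials. Under the unstratified reading it is about 0.02 to 0.09 for factor HR 2 to 4 and about 10% dropout. It grows with prognostic strength and vanishes on average without it. It is most likely to exceed the phi movement when prognostic factors are strong and dropout is low.

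The primary test, its estimate and its type I error are not affected. In these simulations the unstratified shift is toward the null, so it would make the result look less robust, not falsely robust.

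**What to change.** 1. **Step 1.** Add the baseline prognostic factors of the primary analysis to the piecewise-constant hazard model: h(t) = h_0(t) exp(beta_1 X + gamma'Z). Include site only if pooled. In step 3, apply (1 - phi) to the treatment term alone. The factors must be named for this; SAP 3.3.2.2 does not list them, and section 2.3 only gives ulcer presence and ulcer size as examples. If a factor is left out, say why.
2. **Step 5.** State that the stratified log-rank test and stratified Cox model of section 3.3.2.2 are applied to each imputed data set.
3. **Reporting.** Show the phi = 0 row beside the primary result, and read the rest of the grid against phi = 0.

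The cost is a few sentences and slightly more programming. Fewer intervals may be needed: 51 events give 51/6 = 8.5 per interval with six, and 51/4 = about 13 with four. Exact agreement at phi = 0 should not be expected, since imputation noise remains.
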